## E. REPORTING DEADLINES

Event	MDR Article	Method of notification	Time limit for notification to the sponsor
Unrelated AE	NA	In the case report book	No immediate notification
SAEs with a plausible or proven causal link to risk of death/serious illness or injury	Art.80	Declaration form	Immediate notification and within a maximum of 3 days
SAEs with a plausible or proven causal relationship with no risk of death/serious illness or injury	Art.80	Declaration form	
Follow-up of any previously reported events	Art.80	Declaration form	
Serious incident	Arts 87 to 90	Declaration form	

## F. DETAILS OF THE ADVERSE EVENT REPORTING PROCESS

For unrelated adverse events (see Chapter 14.D), the investigator enters the complication directly in the report form.

In all other cases (adverse effects), the investigator completes the dedicated form (see Appendix 4) present in the patient's observation form, taking care to transmit all the requested information relating to the complication. The investigator forwards the form to the person in charge of the study at SERF, whose contact details are specified in the chapter I below and within the time limits (see above). The form can be sent either by fax or by email (form scanned legibly).

Any information concerning the evolution (resolution, worsening of the patient's condition, etc.) of a reported event must also be sent to the person in charge of the study at SERF via the complication declaration form.

If, for any reason, an **adverse reaction** (of any kind) is identified during monitoring and has not been reported to SERF, the adverse event reporting form will be completed from the patient's medical record or case report form if the information is included.

SERF will record on the database of each study the adverse events of the patients participating in the study.

## **G. DETAILS OF THE DEVICE DEFECT REPORTING PROCESS**

This study is an observational study. The reports of defects in the device under study were made by each centre according to their usual procedure.

However, as part of the medium-term follow-up (minimum 4 years postoperative years) of this HF, any defect in the device must be communicated to SERF by the investigator who fills in the dedicated form present in the patient's observation form. The investigator sends the form to the person in charge of the study at SERF, whose contact details are specified in Chapter I. The form can be sent either by fax or by email (form scanned legibly).

## **H. LIST OF FORESEEABLE ADVERSE EVENTS AND EXPECTED ADVERSE REACTIONS OF THE DEVICE**

Known adverse events and reactions related to hip replacement and SAGITTA® EVL R implantation are listed in Chapter 4.

The respective incidences and means of treatment of these complications are known and listed in the clinical evaluation of the device, available upon request.

## **J. INFORMATION RELATED TO THE DATA MONITORING COMMITTEE IF ESTABLISHED**

Not applicable, no data monitoring committee has been established as part of this investigation due to its observational nature.

# **15. VULNERABLE POPULATION**

## **A. DESCRIPTION OF THE VULNERABLE POPULATION TO BE INCLUDED**

No vulnerable populations are planned to be included for this clinical investigation.

## **B. DESCRIPTION OF THE SCREENING PROCESS TO IDENTIFY AND PROTECT VULNERABLE POPULATIONS**

No vulnerable populations are planned to be included for this clinical investigation.

### **C. DESCRIPTION OF THE SPECIFIC PROCESS FOR OBTAINING INFORMED CONSENT**

No vulnerable populations are planned to be included for this clinical investigation.

### **D. DESCRIPTION OF THE SPECIFIC RESPONSIBILITY OF THE ETHICS COMMITTEE**

Not applicable.

### **E. DESCRIPTION OF ANY MEDICAL CARE PROVIDED TO SUBJECTS AFTER HF IS COMPLETED**

Refer to Chapter 6.D.

## **16. PREMATURE TERMINATION OR SUSPENSION OF THE CI**

### **A. CRITERIA AND PROVISIONS FOR PREMATURE TERMINATION OR SUSPENSION OF CLINICAL INVESTIGATION FOR THE ENTIRE INVESTIGATION OR FOR ONE OR MORE SITES**

#### **i. FOR THE ENTIRE INVESTIGATION**

For reasons of safety of the subjects, in particular in the event of suspension of CE marking for a device, resulting in an unacceptable benefit/risk balance, the investigation will be closed prematurely.

#### **ii. FOR ONE OR MORE CENTRES**

- At the initiative of the center or the investigator:
  - o Change of the investigating team that does not allow the continuation of the study and the follow-up of the subjects;
  - o Force majeure (death of the investigator, climatic incidents, etc.)

In this case, the investigator will forward all relevant documentation to SERF.

- At the initiative of the promoter:
  - o Study progress not respected.
  - o Major deviations from protocol and/or regulations and good clinical practices.
  - o Inability of the investigator to include subjects according to the planned schedule.
  - o Lack of patient consent.

### **B. CRITERIA FOR SETTING UP AND BREAKING THE BLINDING CODE DUE TO SUSPENSION OR EARLY TERMINATION OF IC**

Not applicable, the IC is conducted in open-label.

### **C. SUBJECT TRACKING REQUIREMENT**

Any subject with an adverse event should be followed until resolution or stabilization of the event. In all cases (exclusion of the patient from the investigation, premature termination of HF, withdrawal of consent, etc.), the investigator continues to monitor the subject and provide appropriate medical care for his condition.

## 17. PUBLICATION POLICY

### A. REGISTRATION OF THE STUDY IN A PUBLICLY AVAILABLE DATABASE

This clinical investigation will be registered on the EUDAMED database when it is functional, as well as on the public database (ClinicalTrials.gov).

### B. STATEMENT THAT THE RESULTS WILL BE PUBLICLY AVAILABLE

This study may be published. If this is the case, it is envisaged that the preparation of the publication(s) will be carried out by the investigators.

Nevertheless, the results of this study are intended for SERF for the monitoring of its medical devices. In accordance with the legislation in force, it will be possible for the subjects participating in the study to be communicated the results of the investigation to them. The results will be published on the EUDAMED database when it is functional.

### C. STATEMENT OF THE CONDITIONS UNDER WHICH CI RESULTS WILL BE PUBLISHED

If there is a publication of the results, all information provided to the investigator by SERF is strictly confidential. The investigator agrees to use the information to perform the investigation but not for any other purpose without the written permission of SERF. It is understood that it is mandatory to provide SERF with all the data obtained during the investigation.

The information obtained from the CI may be used for further development and may be disclosed to health authorities, other investigators and SERF's designated partners as needed.

These publications will be developed and the list of authors will be determined in accordance with the Harvard Guidelines which state that each author must have a substantial and direct intellectual contribution to the work carried out (Authorship Guidelines):

<http://www.hms.harvard.edu/fa/guide>

With the recommendations of the ICMJE (International Committee of Medical Journal Editors) which indicate that each author must:

- 1) have made a significant contribution to the conception and design of the study, to the collection of data, or to the analysis, or interpretation of the data,
- 2) have participated in the writing of the article or in its proofreading, and
- 3) have given their consent for publication.

The main clinical results, intermediate and final, may be reported at the meetings of the national learned societies and published in the most appropriate international journal. Authors will include the principal investigators, the project methodologist, members of the scientific council, and the local investigators most involved in the project. All investigators will be reported in the list of investigators of the investigation.

In addition, the promoter and the funder(s) of the study will be mentioned in the publications relating to this study.

## APPENDIX 2: PRODUCT INSTRUCTION LEAFLET UNDER REVIEW

## APPENDIX 3: INFORMATION LETTER ON

## APPENDIX 4: SRIA-CIDT REPORTING FORM

## APPENDIX 5: HARRIS HIP SCORE

PAIN			
	No	44	
	Light, occasional, no limitation of activities	40	
	Moderate, no effect on daily activities, may occur after unusual activity, use of minor analgesics	30	
	Moderate, tolerable, some limitations in ordinary activities or at work, taking stronger painkillers	20	
	Severe pain, severe limitation of activities	10	
	Totally disabled, permanent pain even in bed	0	

LIMP			
	No	11	
	Light	8	
	Moderate	5	
	Severe or unable to walk	0	

SUPPORT			
	None	11	
	Rod for long walks	7	
	Cane most of the time	5	
	A crutch/cane	3	
	Two rods	2	
	Two canes or unable to walk	0	

MARKET SCOPE			
Unlimited	11		
30 minutes	8		
10 – 15 minutes	5		
In the house	2		
From bed to chair	0		

ACTIVITIES (shoes, socks)			
With ease	4		
With difficulties	2		
Total incapacity	0		

STAIRS		
Normal, without using the ramp	4	
Normal, using the ramp	2	
Possible but unorthodox	1	
Impossible	0	

TRANSPORT PUBLIC		
Able to use transport	1	
Unable to use transport	0	

SEATED		
Comfortably in a chair for 1 hour	5	
On a chair for 30 minutes	3	
Unable to sit comfortably in a chair	0	

ABSENCE OF VICIOUS ATTITUDES (4 "Yes" = 4 points; Less than 4 "Yes" = 0 points)					
< 30° flessum	Yes		No		
< 10° adductum	Yes		No		
< 10° internal rotation	Yes		No		
Length inequality < 3.2 cm	Yes		No		

MOBILITY (* Standard amplitude)	300° - 211°	210° - 161°	160° - 101°	100° - 61°	61° - 30°	30° - 0°
	Points	5	4	3	2	1
Bending (*140°)						
Abduction (*40°)						
Supply (*40°)						
Belch. External (*40°)						
Belch. Internal (*40°)						

**APPENDIX 6: FORGOTTEN HIP SCORE – SHO12**

Are you aware of your hip...	1pt	2pts	3pts	4pts	5pts
	Never	Hardly ever	Rarely	Sometimes	Often
1. ... in your bed at night?					
2. ... When you sit in a chair for more than an hour?					
3. ... When you walk for more than 15 minutes?					
4. ... when you take a bath or shower?					
5. ... When you travel by car?					
6. ... When you climb the steps of a staircase?					
7. ... When you walk on uneven ground?					
8. ... When you get up from a low sitting position?					
9. ... When you stand for a long time?					
10.... When you do housework or gardening?					
11.... When you are walking or hiking?					
12.... when you practice your favorite sport?					
12b... during your sexual intercourse?					

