#### **Functional Clinical Scores and Ratings**

- *Harris Hip Score*:

The Harris score (HHS) is one of the main functional clinical scores used after hip replacement surgery and evaluates 3 "items" relating to the diseased or operated hip:

- Pain (44 points)
- Function (47 points)
- Mobility (9 points)

For a maximum total score of 100 (minimum score:0), the HHS results will be categorized as follows:

 Harris WH. Traumatic arthritis of the hip after dislocation and acetabular fractures: treatment by mold arthroplasty. An end-result study using a new method of result evaluation. *J Bone Joint Surg Am.* 1969; 51: 737–55.

HHS	
Excellent	90-100
Good	80-89
Correct	70-79
Bad	< 70

The HHS fill grid is available in **Appendix 5**.

- *Forgotten Hip Score (FJS-12):*

The Forgotten Hip Score (SHO-12) is the French version of the FJS-12 (*Forgotten Joint Score*). The objective of this self-questionnaire is to estimate the degree of neglect of the hip and knee prosthesis through 12 questions.

Each item has 5 levels of response:      Never: 0 points

Almost never: 1 point  
Rarely: 2 points  
Sometimes: 3 points  
Often: 4 points

The sum of the items is divided by the number of items and multiplied by 25 to obtain a score out of 100.

The OHSS Fill Grid is available in **Appendix 6**.

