**J. HANDLING MISSING, UNUSED OR ERRONEOUS DATA, INCLUDING ABANDONMENTS AND WITHDRAWALS**

**i. DATA INCLUSION METHODOLOGY**

The simple imputation replacement method can be used if necessary: replace the missing data with a plausible value (mean/median of the variable for the follow-up under consideration, for example) if less than 10% of the data are missing..

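### SHO-12 is defined on 12 questions but collected on a 13-row form, and the protocol does not say how row 12b enters the sum or the divisor

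*Protocol*

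**What the plan says.** Protocol section 6.A.iii, under the functional clinical scores, says of the SHO-12: "The objective of this self-questionnaire is to estimate the degree of neglect of the hip and knee prosthesis through 12 questions". The coding starts at "Each item has 5 levels of response: Never: 0 points" and ends at "Often: 4 points". The scoring rule is "The sum of the items is divided by the number of items and multiplied by 25 to obtain a score out of 100". On this coding a low score means a forgotten hip.

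Appendix 6 is the form on which the answers are collected. Its rows are numbered 1 to 12, row 12 being "when you practice your favorite sport", and are followed by one more tick-box row, "12b... during your sexual intercourse". The form does not say that 12b is an alternative to 12, that only one of them should be ticked, or what to do when neither applies. Its column header gives 1 point for 'Never' up to 5 points for 'Often'.

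SHO-12 is one of the two performance scores named in the secondary objectives (section 5.C.ii). It is also one of the two assessments that the study adds to routine follow-up (section 6.D.i).

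**The concern.** The rule and the form are both in this protocol and do not describe the same questionnaire. The phrase for the divisor can mean 12 (the questions described), 13 (the rows printed) or the number answered. These agree only when the number of rows answered happens to equal the number chosen.

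Rows 12 and 12b concern sport and sexual activity, which will not apply to every patient, so differing numbers of answers must be expected. If the divisor is read as a fixed count, patients with the same level of awareness receive different scores on what is reported as one 0 to 100 scale. An item that is absent from the sum but present in the divisor acts as a 0, which is the code for 'Never'.

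The difference in printed points is a separate conflict between the same two places. It changes the range whatever the item count.

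**Working it through.** **Inputs.** From section 6.A.iii: 12 questions, items 0 to 4, score = sum / divisor × 25, stated maximum 100. From Appendix 6: 13 rows, printed points 1 to 5.

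**Reproducing the stated maximum.** 12 × 4 / 12 × 25 = 100, and 12 × 0 / 12 × 25 = 0. The rule is consistent for exactly 12 items coded 0 to 4.

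**Same patient, different counts.** Take a patient who answers 'Sometimes' (3 points) on every row answered. The score should be 3 × 25 = 75.0 however many rows are answered.

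| Rows answered | Divisor 12 | Divisor 13 | Divisor = rows answered |
|---|---|---|---|
| 11 (12 and 12b blank) | 33/12 × 25 = 68.75 | 33/13 × 25 = 63.46 | 33/11 × 25 = 75.0 |
| 12 (one of them blank) | 36/12 × 25 = 75.0 | 36/13 × 25 = 69.23 | 75.0 |
| 13 (all answered) | 39/12 × 25 = 81.25 | 39/13 × 25 = 75.0 | 75.0 |

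**Maximum (all 'Often', 4 points).**
- Divisor 12: 11 rows give 44/12 × 25 = 91.67, 12 rows give 100, and 13 rows give 52/12 × 25 = 108.33.
- Divisor 13: 12 rows give 48/13 × 25 = 92.31, and 13 rows give 100.
- Divisor equal to rows answered: 100 in every case.

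**How the error scales.** With mean item score L, leaving both rows blank under divisor 12 costs L × 25/12 points: 6.25 at L = 3 and 0 at L = 0. One blank under divisor 13 costs L × 25/13 points: 5.77 at L = 3. Both errors run towards 'forgotten'. Answering all 13 rows under divisor 12 runs the other way, by +6.25 at L = 3.

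**Printed points.** With the form's 1 to 5 points and 12 items over 12, the range is 12 × 1/12 × 25 = 25 to 12 × 5/12 × 25 = 125. Thirteen items over 13 give the same range, so settling the item count alone does not restore a score out of 100.

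**The case against.** The best defence is that the documents point to a harmless reading. The text says 12 questions, the score is called SHO-12, and the extra row is numbered 12b rather than 13. If 12b is simply a variant of item 12, the count is 12 and the range is 0 to 100. The protocol prints no divisor of 12, so 108.3 comes from a combination that it does not prescribe. Item-level missing-data rules are commonly left to a statistical analysis plan, and section 7.J.i already offers one: "The simple imputation replacement method can be used if necessary: replace the missing data with a plausible value". The synopsis also has patient and surgeon complete the questionnaires jointly, which should limit accidental blanks.

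Much of this stands. A reader might infer that, under a divisor of 12, any single unanswered sport or sexual item is scored as 'Never'. That is not so: one blank among 13 rows leaves 12 answers over 12, which is exact. A reader might also infer that the score exceeds 100 by design. It does so only if 13 rows are summed over 12. Nor does the protocol anywhere instruct that a blank be coded 0.

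The defence does not remove the mismatch. The variant reading has to be guessed from a row number, because the form lets both rows be ticked and scored. Even on that reading, a patient with neither row answered has 11 answers, and the divisor is still undefined. Section 7.J.i is optional, applies only below 10% missing, and does not say whether a blank 12b is missing at all. The two sets of item points contradict each other on any reading.

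**Conclusion.** The point holds as a conflict between the scoring rule in section 6.A.iii and the form in Appendix 6. If the divisor is read as a fixed count, neither candidate is right for every ordinary response pattern. Under 12, all 13 rows answered can reach 108.3, and both rows blank turns 75.0 into 68.75. Under 13, one blank turns 75.0 into 69.2. These per-patient figures rest on the 0 to 4 coding and on constant 'Sometimes' answers (constant 'Often' for 108.3). The size varies with the patient's answers and is zero for 'Never' throughout.

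It would be tempting to conclude that the cohort result is flattered, because older or more disabled patients would leave these rows blank. The documents do not support that. They give no rate of unanswered items and no link to age or disability, and under divisor 12 complete responders are shifted in the opposite direction. Neither the size nor the net sign of a cohort shift can be derived.

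The consequence is confined to one secondary descriptive score. It has no preoperative value (section 6.A.iv), no test (section 7.D) and no success threshold (section 7.G). The Kaplan-Meier primary outcome is untouched. The correction is still worth making, because the score is collected once, on paper, at a single visit.

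**What to change.** In section 6.A.iii and on Appendix 6:

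- State that 12 and 12b count as one item, and which answer is used if both are ticked. Using item 12 and keeping 12b as descriptive would be a simple convention. The documents do not give one, so it should be checked against the instrument that the protocol cites.
- Define the divisor as the number of items answered, with a stated minimum below which the score is missing. The documents give no minimum, so the study team must choose it before the data are seen.
- State that a blank is never coded 0.
- In the same edit, make the point values on the form and in the rule identical. The formula gives a score out of 100 only with 0 to 4 points.

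With 0 to 4 points and division by items answered, the range is 0 to 100 for every response pattern. The cost is a short addition to 6.A.iii and a small change to the form. The downside is that a few scores become missing.

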## APPENDIX 7: ENGH SCORE

Fixation					
Appearance of a porous border	 Extensive ≥ 50% -5 pts	 Indeterminate 0 pt	 None +5 pts		
Bone Bridges	 Absence -2.5 pts	 Indeterminate 0 pt	 Presence +5 pts		
Score	..... / 10				
Stability					
Appearance of a smooth border	 Extensive ≥ 50% -3.5 pts	 Indeterminate 0 pt	 None +5 pts		
Pedestal if distal part not locked	 Presence -3.5 pts	 Indeterminate 0 pt	 Absence +2.5 pts		
Calcar modification	 Hypertrophy -4 pts	 Indeterminate 0 pt	 Atrophy +3 pts		
Edging	 Presence -2.5 pts	 Indeterminate 0 pt	 Absence +2.5 pts		
Migration >5mm	 Presence - 5 pts	 Indeterminate 0 pt	 Absence +3 pts		
Appearance of metal particles	 Presence - 5 pts	 Indeterminate 0 pt	 No +1 pt		
Score	..... / 17				
Total Score (Fixation + Stability) .. ...../ 27
